#### Reporting of Excluded Values

Individual values excluded as outliers will be documented in the final report. Approval of the final report will connote approval of the exclusion.

#### **9.3.2 Pharmacokinetic Statistical Methodology**

Pharmacokinetic parameter estimates will be evaluated to delineate effects of injection site. Log-transformed  $AUC(0-\infty)$  and  $C_{max}$  will be evaluated in a linear mixed-effects model with fixed effects for injection site, period, and sequence. Subject nested within sequence will be fitted as a random effect.

For the primary endpoints, the following comparisons will be assessed:

Ratio of  $AUC(0-\infty)$  (90% confidence interval [CI]) and  $C_{max}$  (90% CI) for:

- Upper arm (Test 1) : Abdomen (Reference)
- Thigh (Test 2) : Abdomen (Reference).

Differences will be back-transformed to present the ratios of geometric least squares means and the corresponding 90% CI.

Example SAS code:

```
proc mixed data=DATAIN alpha=0.1;
  by parameter;
  class site period sequence subject;
  model log_pk = site period sequence / cl residual ddfm=kr;
  random subject(sequence);
  lsmeans site / pdiff=control alpha=0.1;
run;
```

For the secondary endpoint, BMI group and the BMI group-by-injection site interaction term will be added to the above model. Subject nested within sequence and BMI group will be fitted as a random effect. The effect of BMI group will be assessed overall, within each injection site, and between injection sites. The comparisons that will be assessed are the following:

Ratio of AUC(0-∞) (90% CI) and Cmax (90% CI) for:

- Low BMI group (Test) : High BMI group (Reference) - Overall
- Low BMI group (Test) : High BMI group (Reference) - Abdomen
- Low BMI group (Test) : High BMI group (Reference) - Upper Arm
- Low BMI group (Test) : High BMI group (Reference) - Thigh
- Upper arm (Test 1) : Abdomen (Reference) - Low BMI
- Upper arm (Test 1) : Abdomen (Reference) - High BMI
- Thigh (Test 2) : Abdomen (Reference) - Low BMI
- Thigh (Test 2) : Abdomen (Reference) - High BMI

Example SAS code:

```
proc mixed data=DATAIN alpha=0.1;
  by parameter;
  class site period sequence subject BMI;
  model log_pk = site period sequence BMI BMI*site / cl residual
ddfm=kr;
  random subject(sequence*BMI);
  lsmeans BMI / pdiff=control alpha=0.1;
  lsmeans BMI*site / pdiff=control alpha=0.1;
run;
```

Injection site will be deemed to show no evidence of a difference if the 90% CI is fully contained within the 0.80 to 1.25 range.

In addition, AUC(0-tlast) will also be analyzed as an exploratory parameter using the same methodology.

The  $t_{\max}$  will be analyzed, analyzed through non-parametric methods for all of the above comparisons. Estimates of the median difference, 90% CIs, and p-values from the Wilcoxon signed rank test will be calculated.

Relationship between exposure to tirzepatide and adiposity/body composition parameters (i.e., skinfold thickness and fat deposition) at the injection sites and waist, thigh, and upper arm circumference may be explored if deemed appropriate. Scatter plots of  $AUC(0-\infty)$  and  $C_{\max}$  versus skinfold thickness, fat percentage, lean mass percentage, waist circumference, thigh circumference, and upper arm circumference will be presented by injection site along with the Pearson's correlation coefficient and the associated p-value.

Additional analyses, such as subgroup analyses, may be carried out if appropriate.

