## 5.4. Scientific Rationale for Study Design

A healthy subject population will allow assessments of the PK, safety, and tolerability of tirzepatide with a reduced likelihood of physiologic variability. Also, healthy subjects are usually devoid of other confounding factors, such as concomitant medication.

In order to minimize any potential period-effect and to allow each subject to act as his/her own control, a randomized, 3-sequence, crossover design has been selected. A washout period of at least 35 days between doses is considered sufficient to minimize any carryover of tirzepatide concentrations from one period into the next period.

This study will be open-label as the study primary endpoint PK measures are objective rather than subjective.

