## **7.2. Method of Treatment Assignment**

Subjects will be randomly assigned to 1 of 3 treatment sequences based on injection site and stratified into 2 groups based on BMI (18.5 to 27.0 kg/m^2 and 27.1 to 45.0 kg/m^2, inclusive) using a computer-generated allocation code.

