##### **10.3.2.2. Pharmacokinetic Statistical Inference**

Pharmacokinetic parameter estimates will be evaluated to delineate effects of injection site. Log-transformed  $AUC(0-\infty)$  and  $C_{max}$  will be evaluated in a linear mixed-effects model with fixed effects for injection site, period, and sequence. Subject nested within sequence will be fitted as a random effect.

For the primary endpoints, the following comparisons will be assessed:

Ratio of  $AUC(0-\infty)$  (90% confidence interval [CI]) and  $C_{max}$  (90% CI) for:

- Upper arm (Test 1) : Abdomen (Reference)
- Thigh (Test 2) : Abdomen (Reference)

Differences will be back-transformed to present the ratios of geometric least squares means and the corresponding 90% CI.

For the secondary endpoint, BMI group and the BMI group-by-injection site interaction term will be added to the above model. Subject nested within sequence and BMI group will be fitted as a random effect. The effect of BMI group will be assessed overall, within each injection site, as well as between injection sites. The comparisons that will be assessed are the following:

Ratio of AUC(0-∞) (90% CI) and Cmax (90% CI) for:

- Low BMI group (Test) : High BMI group (Reference) - Overall
- Low BMI group (Test) : High BMI group (Reference) - Abdomen
- Low BMI group (Test) : High BMI group (Reference) - Arm
- Low BMI group (Test) : High BMI group (Reference) - Thigh
- Upper arm (Test 1) : Abdomen (Reference) - Low BMI
- Upper arm (Test 1) : Abdomen (Reference) - High BMI
- Thigh (Test 2) : Abdomen (Reference) - Low BMI
- Thigh (Test 2) : Abdomen (Reference) - High BMI

Injection site will be deemed to show evidence of equivalence if the 90% CI is fully contained within the 0.80 to 1.25 range.

In addition, AUC(0-tlast) will also be analyzed as an exploratory parameter using the same methodology.

The tmax will be analyzed, using a non-parametric approach for all of the above comparisons. Estimates of the median difference, 90% CIs, and p-values from the Wilcoxon signed rank test will be calculated.

Relationship between exposure to tirzepatide and adiposity/body composition parameters (i.e., skinfold thickness and fat deposition) at the injection sites and waist, thigh, and upper arm circumference may be explored if deemed appropriate.

Additional analyses, such as subgroup analyses, may be carried out if appropriate.

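### The primary model leaves out BMI group, the stratification factor; adding it is a free but small improvement that matters only when subjects are incomplete

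*SAP*

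**What the plan says.** Protocol 7.2: "Subjects will be randomly assigned to 1 of 3 treatment sequences based on injection site and stratified into 2 groups based on BMI".

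Protocol 10.3.2.2 gives the primary PK model "fixed effects for injection site, period, and sequence". SAP 9.3.2 likewise specifies a linear mixed-effects model "with fixed effects for injection site, period, and sequence", and its example code reads "model log_pk = site period sequence / cl residual ddfm=kr". On the random part the SAP says: "Subject nested within sequence will be fitted as a random effect".

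BMI enters only later in SAP 9.3.2: "For the secondary endpoint, BMI group and the BMI group-by-injection site interaction term will be added to the above model". That secondary model reports arm:abdomen and thigh:abdomen ratios within each BMI group. It requests no pooled site ratio adjusted for BMI. No reason is given for leaving the factor out of the primary model, and no sensitivity analysis that includes it is planned.

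Three other points bear on this:
- The PK population (SAP 8, protocol 10.3) keeps anyone with at least one dose and evaluable PK data.
- The sample size sections (SAP 7, protocol 10.1) plan 54 enrolled and at least 36 completers, with about 27 per BMI category and 6 completers per sequence in each category.
- The crossover was chosen, among other reasons, to "allow each subject to act as his/her own control, a randomized, 3-sequence, crossover design has been selected" (protocol 5.4).

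**The concern.** An analysis normally carries the factor that its randomization was stratified by. In a crossover with complete data this hardly matters, because BMI group is fixed within a subject and cancels from every within-subject site contrast. The plan does not count on complete data: up to 18 of 54 subjects (33%) may be incomplete and still be analysed. For such subjects the random-intercept model also draws on comparisons between subjects. Any BMI difference in exposure that is not modelled then sits in the subject variance and costs some precision. If the pattern of missing periods is related both to BMI and to sequence or preceding site, it can also shift a site ratio.

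A BMI difference in exposure is not far-fetched here. The protocol enrolls both groups because adiposity may alter absorption (3.1), and it makes the BMI comparison a secondary objective (section 4). What is at stake is the accuracy of the four primary comparisons with the 0.80 to 1.25 limits.

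**Working it through.** **1. Inputs from the documents** (SAP 7 and 8): 54 enrolled, at least 36 completers, 9 enrolled and 6 completing per BMI-by-sequence cell, CV 19.6%, expected ratio 1.05, limits 0.80 and 1.25, one-sided alpha 0.05.

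**2. Assumptions not in the documents:** low:high exposure ratio 1.25 to 1.5; between-subject SD within a BMI group (σ_b) 0.15 to 0.35 on the log scale; three cyclic sequences; one site effect common to both BMI groups; variances treated as known.

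**3. The plan's own figure.**
- σ_w = √ln(1 + 0.196²) = 0.1942.
- With 36 completers, SE = 0.1942 × √(2/36) = 0.04576.
- TOST power at ratio 1.05 is 98.3% with 68 df, or 98.2% with 34 df. The stated figure of at least 98% is reproduced, without BMI in the model.

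**4. Method.** Generalised least squares for the 3 × 3 design: β̂ = (ΣX′V⁻¹X)⁻¹ ΣX′V⁻¹y, with V = σ_w²I + τ²J.
- With BMI in the model, τ² = σ_b².
- Without it, τ² = σ_b² + δ²/4, where δ is the log of the low:high ratio. δ runs from ln 1.25 = 0.223 to ln 1.5 = 0.405, so δ²/4 runs from 0.012 to 0.041.
- Bias is found by replacing y with the omitted term, ±δ/2 by BMI group.

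**5. Results.**

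| Dropout pattern | SE without versus with BMI | Bias in a site ratio, without BMI |
|---|---|---|
| None | 0.03737 in both (= 0.1942 × √(2/54)) | 0 |
| 18, even: in each cell, 2 leave after period 1 and 1 after period 2 | 0.0429–0.0436 versus 0.0427–0.0435; 0.1%–1.3% larger | 0 |
| 18, all low BMI, equal across sequences | 0.1%–1.1% larger | 0 |
| 3 low-BMI subjects leave after a first-period arm dose | not the issue here | about 0.15%–0.5% (arm) |
| Worst patterns found that keep 6 completers per cell | 0.1%–2.0% larger | 0.4%–1.4% |

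The last row comes from a search, and the worst pattern for SE is not the worst for bias. With BMI in the model the bias is 0 in every row.

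**6. Why the third row shows no bias.** Each site occurs once in each period across the three sequences. If low-BMI subjects thin out equally in all sequences, every site loses them equally, and the shift goes into the period effect. This holds even though 18 losses from 27 leave only 3 completers per low-BMI sequence, below the planned 6.

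**7. Power.** With 18 even dropouts, power at ratio 1.05 differs by at most 0.12 points (0.9906 without BMI, 0.9918 with it).

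**8. Scale of the largest bias.** ln 1.014 = 0.0139, against an SE of about 0.0415 in that pattern, is 0.0139/0.0415 = 0.33 SE. The distance from the planned ratio to the nearer limit is ln(1.25/1.05) = 0.174, or 0.174/0.0415 = 4.2 SE.

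**The case against.** The strongest reply is that the design already removes the usual reason to adjust. Each subject is their own control, and the random subject effect absorbs most of a BMI difference. The precision gain is mostly under 1% of a standard error. Bias needs dropout that depends on BMI and also on sequence or preceding site, and nothing in the documents predicts that: dose, formulation and autoinjector are the same at every site (Table GPHI.2). The secondary model already gives site ratios within each BMI group, where a distortion could be looked for. All of this stands, and it is why the point is a refinement only. It does not supply a reason for omitting the term, and the secondary model yields no pooled adjusted ratio.

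A reader might infer two stronger things. The first is that BMI-related dropout by itself contaminates the site ratios. It does not, as step 6 of the working shows. The second is that the equivalence test is unsafe. In a pattern with 12 low-BMI subjects leaving straight after the arm dose, bias is 0.4% to 1.2%, and the error rate at a true ratio of 0.80 rises from 5% to about 7% to 9% in the cases computed. But only the two sequences with the arm in period 1 or 2 can lose subjects this way. They would keep 18 − 12 = 6 low-BMI completers against a planned 12, so the pattern breaks the retention plan. The worst bias within planned retention (0.33 SE) could inflate the error rate similarly, but again only for a true ratio lying on a limit, while the plan expects 1.05. The documents support neither the dropout pattern nor a ratio at the limit.

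**Conclusion.** The point holds as a minor one. The primary model omits the stratification factor, and with the incompleteness the plan allows this has a small effect that can be avoided: a standard error about 0.1% to 1.3% larger with even dropout and up to about 2% larger at worst, and a bias of at most about 1.4% in a site ratio under planned retention. The bias arises only when dropout is related to BMI and also to sequence or preceding site. With complete data the effect is nil, and the stated power is unaffected.

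The sizes rest on the assumed exposure ratio of 1.25 to 1.5 and between-subject log SD of 0.15 to 0.35; a smaller BMI difference would shrink them. They also assume that the site effect is the same in both BMI groups. If it is not, a BMI main effect does not correct selective dropout; the by-group ratios of the secondary model address that case.

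**What to change.** In SAP 9.3.2, add BMI group as a fixed main effect in the primary model: put `BMI` in the class statement and use `model log_pk = site period sequence BMI`, keeping the existing options. Make the matching change in protocol 10.3.2.2. If only the SAP is changed, its section 11, which now records no changes from the protocol analyses, must say so. Writing the random term as `subject(sequence*BMI)` is for consistency with the secondary model only; with unique subject identifiers it defines the same effect.

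The cost is one between-subject degree of freedom and a short text change. Site contrasts lose nothing with complete data. In one lopsided dropout pattern the adjusted standard error was larger by under 0.1% (0.04151 versus 0.04147), in exchange for removing the bias.

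The change should be specified in advance, since the study is open-label and data may be accessed while it runs (protocol 10.3.4, SAP 10). If the sponsor prefers to keep the primary model as it is, the BMI-adjusted model can be pre-specified as a sensitivity analysis.

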### Rationale:

Study I8F-MC-GPHI (GPHI) will investigate the effect of injection site on the relative bioavailability of a single 5 mg dose of tirzepatide injected subcutaneously (SC) into the upper arm (Test 1) or thigh (Test 2) compared to SC injection into the abdomen (Reference). During previous Phase 1 and Phase 2 clinical trials, tirzepatide has been administered by SC injection into the abdomen. However, patients in clinical practice may prefer to self-administer tirzepatide at different body sites. In addition, a difference in adiposity and/or absorption profile may lead to increased variability and suboptimal glycemic control. This will be explored in the current study by enrolling subjects with both low and high body mass indices (BMI).

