## 7. SAMPLE SIZE JUSTIFICATION

Approximately 54 subjects will be enrolled to ensure that at least 36 evaluable subjects complete the study, with at least 12 subjects completing per treatment sequence. With 36 subjects, we expect the two one-sided t-tests (TOST) for equivalence applied to the log-normal mean ratio to have a power of at least 98% for each of the 4 tests on the primary objective. This assumes a nominal expected mean ratio of 1.05, a coefficient variation of 19.6%, and significance level of 0.05 of each one-sided test when testing against an upper limit of 1.25 and lower limit of 0.80. The source of the choice of coefficient of variation is from the final results of study I8F-MC-GPGE. For balance and the evaluation of the secondary objective of effect of BMI, the 54 subjects will be enrolled according to their BMI category such that each category enrolls approximately 27 subjects and retains 6 completers per treatment sequence.

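### The secondary BMI model pools one residual variance over Low and High BMI, so the within-BMI site ratios would have mis-sized 90% CIs if residual variability differs by BMI

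*SAP*

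**What the plan says.** The synopsis rationale of the protocol states that "a difference in adiposity and/or absorption profile may lead to increased variability and suboptimal glycemic control. This will be explored in the current study", the means being enrolment of both BMI groups. Protocol 3.1 repeats this and adds skinfold and DEXA measurements.

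SAP 9.3.2 (and Protocol 10.3.2.2) extends the primary mixed model for the secondary endpoint. BMI group and BMI-by-site enter as fixed effects, and "Subject nested within sequence and BMI group will be fitted as a random effect". The fixed part of the example code is "model log_pk = site period sequence BMI BMI*site / cl residual". It is followed by a single random subject term, with no REPEATED statement and no GROUP= option. One between-subject variance and one residual variance therefore serve both BMI groups.

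Eight secondary comparisons are listed for each of AUC(0-∞) and Cmax. Four are Low:High ratios (overall and by site). Four are site:abdomen ratios within a BMI group. The 0.80 to 1.25 rule comes after this list and is not limited to the primary comparisons.

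SAP 7 gives one CV for the whole study: "This assumes a nominal expected mean ratio of 1.05, a coefficient variation of 19.6%, and significance level of 0.05 of each one-sided test". For the BMI groups, "each category enrolls approximately 27 subjects and retains 6 completers per treatment sequence", which is 6 × 3 = 18 completers per group.

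SAP 9.1 and 9.3.1 also plan geometric CV% for AUC and Cmax, by injection site and BMI group.

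**The concern.** The rationale raises the possibility that variability rises with adiposity, and the model used to compare BMI groups assumes equal variability. For a site:abdomen contrast within one BMI group, the correct standard error depends on that group's own residual variance. The planned model uses the average over both groups. The Kenward-Roger option adjusts standard errors and degrees of freedom within the fitted covariance structure; it does not correct a structure that is wrong.

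If residual variance is larger in High BMI, the High-BMI intervals are too narrow and fall inside 0.80 to 1.25 too readily. The Low-BMI intervals are too wide. The anti-conservative error would then lie in the group the rationale is concerned about. The plan also would not report the residual within-subject CV by group, which is what sizes these intervals.

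**Working it through.** **Reproducing the plan's figure.** SAP 7 claims "a power of at least 98% for each of the 4 tests on the primary objective" with 36 completers, mean ratio 1.05, CV 19.6%, one-sided 0.05 and limits 0.80 to 1.25. On the log scale, SD = √ln(1 + 0.196²) = 0.1942 and SE = 0.1942 × √(2/36) = 0.0458. Residual df = 108 observations − 36 subjects − 2 period − 2 site = 68. Integrating TOST power over the chi-square distribution of the residual variance gives 98.3%. The stated figure stands.

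**Within one BMI group, equal variances.** With 18 completers, SE = 0.1942 × √(2/18) = 0.0647. Residual df = 108 − 36 − 2 − 4 = 66. Coverage is 90%, and power at a ratio of 1.05 is 84%.

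**Unequal variances.** Assumption: the documents give no CV by BMI group, so the split is varied with the average held near 19.6%. The formulas are:

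- group SD = √ln(1 + CV²)
- pooled SD = √[(SD_Low² + SD_High²)/2]
- coverage ≈ P(|Z| < t(0.95, df) × pooled SD / group SD)

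Worked case, CV 17% and 22%: the SDs are 0.1688 and 0.2174, and the pooled SD is √[(0.02849 + 0.04726)/2] = 0.1946. With t(0.95, 66) = 1.668:

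- High: 1.668 × 0.1946/0.2174 = 1.493, coverage 86.5%
- Low: 1.668 × 0.1946/0.1688 = 1.923, coverage 94.6%

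This shortcut treats the pooled SD as known. Averaging over its sampling variation gives 86.0% and 94.1%. The table shows averaged values; 18 and 27 per group agree to the rounding shown.

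| CV Low / High | SD ratio | Coverage Low | Coverage High | High interval should be wider by |
|---|---|---|---|---|
| 19.6% / 19.6% | 1.00 | 90% | 90% | 0% |
| 17% / 22% | 1.29 | 94% | 86% | 12% |
| 15% / 23.5% | 1.55 | 97% | 83% | 19% |
| 12% / 25% | 2.06 | 99% | 80% | 27% |

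**Check by simulation.** The 3×3 design was simulated with 18 completers per group and average variance fixed at CV 19.6%. At SD ratios of 1.25, 1.5 and 2, High coverage was 86%, 84% and 81%, and Low coverage 94%, 96% and 99%. The one-sided error at a true ratio of 1.25 was 6.8%, 8.0% and 9.7% in High and 3.1%, 1.8% and 0.6% in Low, against a nominal 5%.

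**With separate residual variances.** Coverage returns to 90% in both groups at every ratio. At an SD ratio of 1.25 and a mean ratio of 1.05, power moves from 87% to 91% in Low and from 81% to 75% in High; the lower High figure is the honest one.

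**Cost if the variances are equal.** Each group then relies on roughly its own df: t(0.95, 50)/t(0.95, 102) = 1.676/1.660 = 1.010 with 27 per group, and t(0.95, 32)/t(0.95, 66) = 1.694/1.668 = 1.015 with 18.

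**Low:High ratios.** With n per group, the variance within a site is the sum of the two groups' total variances divided by n. The pooled value doubled and divided by n is the same number, so these four comparisons are little affected when the groups are balanced.

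**The case against.** The strongest reply is that a common residual variance is a conventional choice and that no objective or endpoint concerns variance. The protocol promises to explore variability by enrolling both groups, not to test it. The secondary objective is relative bioavailability by BMI. The exploratory objective, adiposity against exposure, has scatter plots and correlations. All of this stands, and the absence of a variance test is not a defect.

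A reader might infer that the trial will end with nothing on variability by BMI. The documents do not support that: geometric CV% by site and BMI group is planned. It is a total CV, however. Each subject has one injection per site, so it includes between-subject spread, which cancels from the site contrasts in complete data. It neither gives the residual CV nor repairs the intervals.

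It is also fair that the rationale's wording could mean more spread between patients or between sites, and only higher residual variance in High BMI produces the error described here. The quoted sentence about the subject effect does not itself fix the residual structure; the code does, and it is labelled as an example. But the text names no group-specific variance either. The MODEL statement requests residual diagnostics without saying what would follow from them, and the provision for additional analyses names no variance model.

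**Conclusion.** The point holds as a conditional weakness in four secondary ratios for each of AUC(0-∞) and Cmax. If residual CV is about 17% in Low and 22% in High BMI, the nominal 90% intervals cover about 94% and 86%; at 15% and 23.5%, about 97% and 83%. With equal variances nothing is wrong. The results assume complete, balanced data and an average CV near 19.6%; the split between groups is not in the documents. The 80% figure for High needs a variance ratio above 4 and should be read as an extreme.

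Two stronger conclusions are tempting and unsupported. One is that the High-BMI intervals are in fact too narrow; the documents give no evidence that the variances differ. The other is that the study's main conclusion is at risk; the primary comparisons do not use this model, and their 98% power reproduces. This is an inexpensive improvement to a secondary analysis, worth making because the protocol itself raises the possibility.

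**What to change.** In the secondary PROC MIXED model add `repeated / group=BMI`, keep `ddfm=kr`, and take the four within-BMI site:abdomen ratios from that model. At the least, prespecify it as a sensitivity analysis beside the pooled model. Report the residual CV with a confidence interval for each BMI group, noting that without replicate dosing it includes any subject-by-site interaction.

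A formal variance test is not needed. With 18 completers per group, a two-sided 10% F test has only about 35% power at an SD ratio of 1.25 and 74% at 1.5, so the estimates with their intervals are more useful. A BMI-specific variance on the random subject term would hardly change these four ratios in complete data.

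The cost is one statement of code, one extra variance parameter and one small table. If the groups do not differ, the intervals widen by about 1% (27 per group) to 1.5% (18 per group). If High BMI is more variable, its intervals lose apparent power, as they should.

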**Table GPHI.1. Objectives and Endpoints**

Objectives	Endpoints
Primary To determine the relative bioavailability of SC tirzepatide 5-mg injection into the thigh and upper arm compared to the abdomen.	AUC(0-∞) and C max
Secondary To determine the relative bioavailability of SC tirzepatide 5-mg injection in subjects with different BMIs.  To evaluate the safety and tolerability of SC tirzepatide 5-mg injection.	AUC(0-∞) and C max  Incidence of TEAEs
Exploratory To explore the relationship between adiposity at injection site with tirzepatide exposure.	AUC(0-∞) and C max

Abbreviations: AUC(0-∞) = area under the concentration versus time curve from zero to infinity; BMI = body mass index; Cmax = maximum drug concentration; SC = subcutaneous; TEAE = treatment-emergent adverse event.

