### **3. INTRODUCTION**

This SAP has been developed after review of the Clinical Study Protocol (final version dated 27 June 2019).

This SAP describes the planned analysis of the pharmacokinetic (PK), safety and tolerability data from this study. A detailed description of the planned TFLs to be presented in the clinical study report (CSR) is provided in the accompanying TFL shell document.

The intent of this document is to provide guidance for the statistical and PK analyses of data. In general, the analyses are based on information from the protocol, unless they have been modified by agreement between Eli Lilly and Company and Covance Early Clinical (EC) Biometrics. A limited amount of information concerning this study (e.g., objectives, study design) is given to help the reader's interpretation. This SAP must be signed off prior to first subject administration for this study. When the SAP and TFL shells are agreed upon and finalized, they will serve as the template for this study's CSR.

This SAP supersedes the statistical considerations identified in the protocol; where considerations are substantially different, they will be so identified. If additional analyses are required to supplement the planned analyses described in this SAP, they may be performed and will be identified in the CSR. Any substantial deviations from this SAP will be agreed upon between Eli Lilly and Company and Covance EC Biometrics and identified in the CSR. Any minor deviations from the TFLs may not be documented in the CSR.

This SAP is written with consideration of the recommendations outlined in the International Conference on Harmonisation (ICH) E9 Guideline entitled Guidance for Industry: Statistical Principles for Clinical Trials and the ICH E3 Guideline entitled Guidance for Industry: Structure and Content of Clinical Study Reports.

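### For tmax the plan names only the paired Wilcoxon signed rank test, which does not fit four of the ten listed comparisons: the Low:High BMI contrasts between different subjects

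*SAP*

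**What the plan says.** SAP 9.3.2 lists two primary comparisons of injection site (upper arm and thigh, each against abdomen) and eight secondary ones. The secondary list opens with "Low BMI group (Test) : High BMI group (Reference) - Overall", gives the same BMI contrast at each of the three sites, and ends with the two site contrasts inside each BMI group. For AUC(0-∞) and Cmax these are estimated from linear mixed models. In the secondary model, "Subject nested within sequence and BMI group will be fitted as a random effect".

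The tmax analysis follows. It is described as non-parametric and is to be done "for all of the above comparisons. Estimates of the median difference, 90% CIs, and p-values from the Wilcoxon signed rank test will be calculated". Protocol 10.3.2.2 has the same scope and names the same single test.

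On how BMI enters the design, Protocol 7.2 states: "Subjects will be randomly assigned to 1 of 3 treatment sequences based on injection site and stratified into 2 groups based on BMI". The two BMI ranges, 18.5 to 27.0 and 27.1 to 45.0 kg/m², do not overlap. SAP section 11 reports no changes from the analyses in the protocol.

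**The concern.** The signed rank test works on one difference per pair. A crossover supplies that difference for a site contrast, because the same subject is injected at both sites. It supplies none for a BMI contrast, because each subject belongs to one BMI group only. Applied to the full list, the sentence promises p-values that the named test cannot validly give for the BMI contrasts.

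If the wording stays, the analyst must choose another test later. For the overall contrast the analyst must also choose how to treat repeated values from one subject. The study is open-label, and SAP section 10 allows data to be accessed while it is ongoing, so these choices are better fixed in advance.

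**Working it through.** The plan gives no numerical figure for tmax to reproduce. The power statement in SAP section 7 concerns the four primary tests and has no bearing here. The check is a count and a classification of the comparisons listed in SAP 9.3.2.

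**Step 1: count.** 2 primary + 8 secondary = 10 comparisons.

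**Step 2: classify by whether the same subject contributes to both sides.**

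| Comparisons | Number | Same subjects on both sides? | Signed rank test applies? |
|---|---|---|---|
| Upper arm:abdomen and thigh:abdomen, all subjects | 2 | Yes | Yes |
| The same two contrasts within low BMI and within high BMI | 2 × 2 = 4 | Yes | Yes |
| Low:High BMI at abdomen, upper arm, thigh | 3 | No | No |
| Low:High BMI overall | 1 | No | No |

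Within-subject: 2 + 4 = 6. Between-subject: 3 + 1 = 4. Check: 6 + 4 = 10.

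**Step 3: look for any pairing of low with high BMI subjects.** There is none. BMI group is a randomisation stratum (Protocol 7.2), and neither document describes matching across strata. The SAP's own secondary model nests subject within sequence and BMI group, so for AUC(0-∞) and Cmax it already treats BMI as a between-subject factor. Equal group sizes are not guaranteed either: SAP section 7 plans that "each category enrolls approximately 27 subjects and retains 6 completers per treatment sequence", which is about 27 enrolled and 6 × 3 = 18 completers per group as targets. Even with equal groups, any pairing would be arbitrary and the result would depend on it.

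**Step 4: look for another named test.** Neither document mentions a rank-sum, Mann-Whitney or other two-sample test for tmax.

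**Step 5: the overall contrast.** Each subject has up to three tmax values, one per period. With 18 completers in a BMI group that is 18 × 3 = 54 values from 18 subjects, which are not 54 independent observations. The mixed model handles this through the random subject effect. The tmax text has no counterpart: it does not say whether values are averaged, otherwise summarised or pooled, or what is done with subjects who lack a site.

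**Step 6: estimate and interval.** The sentence promises a median difference and a 90% CI without saying which estimator or interval method. That gap applies to all ten comparisons, including the six for which the test is right.

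**The case against.** The strongest reply is that almost nothing turns on this. Table GPHI.1 assigns AUC(0-∞) and Cmax as the endpoints for the objective "To determine the relative bioavailability of SC tirzepatide 5-mg injection in subjects with different BMIs". tmax is not an endpoint of any objective, and Protocol 10.3.2.1 lists it among parameters whose reporting is optional. The 0.80 to 1.25 criterion applies to ratios, and no decision rule is attached to tmax. All of this stands, and it limits the point to minor.

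A second reply is that the lead-in speaks of non-parametric methods in general, which leaves room for a two-sample rank test, and that a programmer would notice the problem. SAP section 3 requires substantial deviations to be agreed and identified in the clinical study report. It also refers to table, figure and listing shells, which were not available for this review and may say more. This softens the point but does not remove it: the next sentence names one test, for every comparison, and that test is the wrong kind for four of them. A substitution at programming would also leave the overall contrast undefined.

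A reader might go further and infer that the overall contrast would be restricted to subjects with tmax at all three sites, at a cost in sample size. SAP section 7 does say that "54 subjects will be enrolled to ensure that at least 36 evaluable subjects complete the study", so incomplete subjects are foreseen. But neither document imposes that restriction on tmax, so a loss calculated from it would measure one possible way of filling the gap and not a defect in the plan.

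**Conclusion.** The point holds and is minor. Four of the ten tmax comparisons are assigned a paired test although they compare unmatched groups, and no two-sample test is named for them. One of the four, the overall contrast, also lacks a rule for reducing up to three values per subject to one. As written this is a wrong specification for those four and not merely missing detail.

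A reader might infer that the secondary BMI objective as a whole is compromised. It is not: its endpoints are AUC(0-∞) and Cmax, analysed by a mixed model that treats BMI group as between-subject. The primary analysis and the sample size do not change. Nor should the six site contrasts be read as fully specified: their test is appropriate, but their estimator and interval are unstated.

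The conclusion rests on the protocol and SAP text alone, and on there being no matching of low to high BMI subjects, since none is described.

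**What to change.** In SAP 9.3.2, replace the single tmax sentence with wording to this effect:

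- For the six within-subject site contrasts, keep the Wilcoxon signed rank test, and state that the median difference and 90% CI are the Hodges-Lehmann estimate and interval that match it.
- For the Low:High BMI contrasts at abdomen, upper arm and thigh, use the Wilcoxon rank-sum test with the Hodges-Lehmann shift and its 90% CI, in all subjects of the Pharmacokinetic population who have a tmax at that site.
- Drop the overall Low:High contrast for tmax. The three site-specific contrasts already cover the BMI question, and dropping it removes the need for a rule to combine values within a subject.

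Replace the statement in SAP section 11 that nothing has changed with a line recording this. The SAP is the right place for the change: "This SAP supersedes the statistical considerations identified in the protocol; where considerations are substantially different, they will be so identified".

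The cost is a few sentences in SAP 9.3.2 and one line in section 11, with no additional data or subjects. The only loss is that one non-endpoint tmax contrast is no longer reported.
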